6.3 Feasibility and Futility Considerations

In Study 20210061 we aim to collect data on approximately 15 to 30 patients initiating BLINCYTO® treatment for Ph+ R/R B-cell precursor ALL after commercial availability of BLINCYTO® in China. Amgen intends to select large centers in China, as it is anticipated these sites treat the most patients with R/R B-cell precursor ALL. The rationale for the sample size is based on the incidence of Ph+ status among B-cell precursor ALL patients, the prior knowledge from the global clinical trial (Study 20120216) for the treatment of Ph+ R/R B-cell precursor ALL with BLINCYTO®, and the expected clinical use of BLINCYTO® in China. The global clinical trial enrolled 45 Ph+ ALL patients from centers in Europe and the United States indicating that the estimated sample size is achievable. Medical records have been shown to contain the relevant data for this study for exposures, covariates, and outcomes among ALL patients in China (Ma, 2018). Site feasibility has identified out of 30 polled sites that at least half have an interest in participating in the study. This should be sufficient to hit the target sample size of at least 15 patients enrolled.

Further consideration for feasibility of enrollment of Ph+ patients can be drawn from two additional real-world evidence studies. Study 20150136 is a post marketing commitment real-world study of BLINCYTO® safety and effectiveness, utilization, and treatment practices in routine clinical practice in countries in Europe. The study objectives were to characterize the safety profile of BLINCYTO® by characterizing adverse events, and to estimate the frequency and type of medication errors identified in patient charts. The latest interim analysis reported 144 Ph- R/R patients and 10 Ph+ R/R patients. Further reference is made to a non-Amgen sponsored study conducted to assess BLINCYTO® in a retrospective multicenter study at 11 academic institutions in the United States (Badar, 2020). The study enrolled B-cell ALL patients age ≥ 18 years at the time of BLINCYTO® administration, and who received drug outside of clinical trials. Medical records were reviewed to collect demographic, patient-related, disease related and clinical outcome data. These patients were evaluated for response, RFS, OS from the time of BLINCYTO® initiation, and toxicities. The study analyzed the data of 239 ALL patients. Overall, 61 (25%) with Ph+ were enrolled, of which 55 were diagnosed with R/R Ph+ B-cell ALL and received BLINCYTO®. Among the Ph+ patients, 29 patients received BLINCYTO® in combination with a TKI. Typical duration of treatment from the global perspective with BLINCYTO® has been a median of 2 cycles, 28 days/cycle.

6.4 Statistical Inference (Estimation or Hypothesis[es])

There is no formal hypothesis to be tested. The study is descriptive in nature and will assess effectiveness and safety outcomes.

7. Research Question and Objectives

7.1 Primary

- To estimate the percentage of patients with CR/CRh within two cycles of treatment with BLINCYTO® in Chinese adults with Ph+ R/R B-cell precursor ALL
- To estimate the incidence of adverse EOI (recorded within 6 months of first infusion of BLINCYTO®)

7.2 Secondary

- To describe the use of BLINCYTO® and TKIs in clinical practice
- To estimate the occurrence of alloHSCT after BLINCYTO® treatment
- To estimate the percentage of patients achieving MRD negative status after CR/CRh
- To estimate OS at 6 months
- To estimate RFS at 6 months

8. Research Methods

8.1 Study Design

This is a retrospective observational study in the post-marketing setting using medical record review.

8.2 Setting and Study Population

The study population will include adult patients of Chinese descent (≥ 18 years at the initiation of BLINCYTO®) treated with BLINCYTO® for Ph+ R/R B-cell precursor ALL at participating clinical sites in China. We aim to collect data on approximately 15 to 30 patients initiating BLINCYTO® treatment for Ph+ R/R B-cell precursor ALL after commercial availability of BLINCYTO® in China. Patient-level data will be obtained by abstraction of data from existing medical records at participating study sites.

R/R is defined as follows:

Primary refractory ALL is defined by absence of CR after standard induction therapy.

Refractory relapse is defined by lack of CR after salvage therapy.

First relapse is defined if the patient achieved a CR during upfront therapy and then relapsed during or after completion of therapy.

Second relapse or later relapses are defined as relapse after achieving a second complete remission in first salvage or later salvage therapies.

8.2.1 Study Period

BLINCYTO® was approved in for use in China on December 2, 2020. The eligible treatment with BLINCYTO® should occur after December 2, 2020. Data abstraction of eligible medical records retrospectively will occur at a minimum of 6 months after first infusion of BLINCYTO® treatment for each patient. Data collection will occur at one point in time. The enrollment period will be approximately 6 months from first patient enrolled (FSE) on the study.

End of Study (EOS) is defined as the last chart abstraction for the last patient enrolled.

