8.3.2 Outcome Assessment

Primary Outcomes

- CR/CRh rate within two cycles of BLINCYTO®. CR is defined as: < 5% bone marrow (BM) blasts, no evidence of extramedullary disease (EMD) and full recovery of peripheral blood counts defined as, platelets $\geq 100\,000/\mu\text{L}$, and absolute neutrophil count (ANC) $\geq 1000/\mu\text{L}$; CRh is defined as a CR with partial recovery of peripheral blood counts defined as platelets $> 50\,000/\mu\text{L}$ and $< 100\,000/\mu\text{L}$ and ANC $> 500/\mu\text{L}$ and $< 1000/\mu\text{L}$.
- Incidence of Adverse EOI. EOI are defined as: Cytokine release syndrome (CRS), BLINCYTO® associated neurological adverse event, and infection.

Secondary Outcomes

- BLINCYTO® use will be defined by BLINCYTO® treatment measured by number of cycles and duration of cycles. BLINCYTO® monotherapy and concomitant therapy with TKIs will be described.
- Occurrence of alloHSCT after BLINCYTO® treatment
- MRD status by flow cytometry or Polymerase Chain Reaction (PCR) within two cycles. MRD negativity is defined as: $<10^{-4}$ leukemic cells.
- OS is defined as the time from first infusion of BLINCYTO® until death due to any cause.
- RFS is defined for subjects who achieved CR/CRh within two cycles, as the time from first onset of CR/CRh until date of first documented relapse, or death due to any cause, whichever occurs first.

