applicable. The number (percentage) of patients with BLINCYTO® monotherapy or concomitant therapy with TKIs will be summarized.

- The proportion and Clopper-Pearson 95% CI of patients who undergo alloHSCT will be estimated after BLINCYTO® treatment. Additional summary by best treatment response status will be provided.
- MRD status will be summarized descriptively by each category. The proportion and Clopper-Pearson 95% CI of MRD negativity will be estimated.
- OS will be estimated by K-M method, with patients censored on the last documented visit/assessment/contact date from the charter review if not dead. Landmark survival rates with associated 95% CIs at 3- and 6-months after first infusion of BLINCYTO® will be provided if estimable.
- RFS will be estimated by K-M method and only for patients who achieved CR/CRh within two cycles of BLINCYTO®. Patients with no documented relapse or death will be censored at the latest date indicating the subject remains in CR/CRh.

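### The alloHSCT proportion has no time horizon, so it depends on start dates and on when charts were read; a smaller mismatch affects 6-month RFS

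*Protocol*

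**What the plan says.** **Follow-up.** Protocol 8.2.1 sets one timing rule: "Data abstraction of eligible medical records retrospectively will occur at a minimum of 6 months after first infusion of BLINCYTO® treatment for each patient". It adds: "Data collection will occur at one point in time". Sections 8.2.3.1 and 8.2.6 repeat the 6-month minimum, and 8.2.6 admits first infusions from 2 December 2020. Enrolment lasts about 6 months. No upper limit on follow-up is set. Under 8.2.3.1, nothing is collected after a patient enters a clinical trial.

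**alloHSCT.** The endpoint table in the Abstract and 8.3.2 define it as a transplant after BLINCYTO, with no window. The analysis in 8.7.2.4 reads: "The proportion and Clopper-Pearson 95% CI of patients who undergo alloHSCT will be estimated after BLINCYTO® treatment". A breakdown by best response is added.

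**RFS.** The objective in 7.2 is "To estimate RFS at 6 months". Its clock is set in 8.3.2: "RFS is defined for subjects who achieved CR/CRh within two cycles, as the time from first onset of CR/CRh". Under 8.7.2.4 it is estimated by Kaplan-Meier, and "Patients with no documented relapse or death will be censored at the latest date indicating the subject remains in CR/CRh".

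**For contrast.** Events of interest are restricted to 6 months from first infusion (7.1, 8.7.2.4), and OS runs from first infusion with 3- and 6-month landmarks. Both fit the minimum follow-up.

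**The concern.** A binomial proportion is easy to interpret when every patient has had the same time in which the event could be seen. Here a patient who started soon after approval may have had two and a half years or more, and a recent starter 6 months. A patient not yet transplanted when the chart was read counts the same as one who never will be. So does a patient whose record stops at trial entry or last contact. Two cohorts with identical transplant behaviour would give different figures if their start dates differed. The open wording also counts a transplant reached only after further salvage therapy.

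The figure will be read closely: 6.2 calls alloHSCT the only curative option in relapsed or refractory disease, and Section 12 sends the results to the Chinese regulator.

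The lesser issue is that RFS and the follow-up minimum have different time origins. A relapse-free responder read at the minimum is always censored before the 6-month RFS landmark.

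**Working it through.** The protocol gives no figure to reproduce here, because the study size rests on feasibility. The check is date arithmetic, with 1 month = 365.25/12 = 30.44 days.

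**1. alloHSCT opportunity**
- Shortest nominal opportunity: 6 months (8.2.1). Death, trial entry or loss of contact can make it shorter.
- Longest: 2 December 2020 (8.2.6) to 22 June 2023 (Investigator's Agreement) is 932 days, and 932/30.44 = 30.6 months. This assumes that abstraction does not precede the protocol date.
- A chart read 6 months later gives 30.6 + 6 = 36.6 months.
- Ratio of longest to shortest: 30.6/6 = 5.1, up to 36.6/6 = 6.1.

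**2. What that can do to the proportion (illustration)**

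The inputs are assumed and are not in the protocol: 40% ever transplanted, exponential time to transplant with median m months. Share seen by month t = 0.40 × (1 − 2^(−t/m)).

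| m (months) | seen at 6 months | seen at 30.6 months |
|---|---|---|
| 3 | 30% | 40% |
| 6 | 20% | 39% |
| 9 | 15% | 36% |

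Each column supposes that all patients share one follow-up time, so a real cohort lies between the two. For scale, 12 of 30 (40%) has a Clopper-Pearson 95% interval of 22.7% to 59.4%, a half-width of about 18 points. The extreme shift at m = 6 is 39 − 20 = 19 points, about the same size. The interval does not reflect it.

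**3. RFS follow-up for a responder read at the minimum**

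Available RFS time = 6 months − time from first infusion to CR/CRh. For cycle length, 6.3 says: "Typical duration of treatment from the global perspective with BLINCYTO® has been a median of 2 cycles, 28 days/cycle".
- Response at day 28: 183 − 28 = 155 days (5.1 months).
- Response at day 56: 183 − 56 = 127 days (4.2 months).
- Response at day 84 (assumes gaps between cycles): 6 − 84/30.44 = 3.2 months.

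All fall short of 183 days, and censoring at the last date in remission can shorten them further.

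**4. How many responders that affects**
- Responders: the prior trial's rate in 6.2 is 35.6%. 15 × 0.356 = 5.3 and 30 × 0.356 = 10.7, so about 5 to 11.
- If starts were evenly spread (assumed) and charts read at A months after approval, eligible starts span A − 6 months. The share falling short is (response day/30.44)/(A − 6).
- A = 30.6: 3.7%, 7.5% and 11.2% for days 28, 56 and 84. A = 36.6: 3.0%, 6.0% and 9.0%.
- Expected number: from 5.3 × 0.030 = 0.2 to 10.7 × 0.112 = 1.2 responders. This is an upper figure, since only those still alive and relapse-free are censored early.

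**The case against.** **On alloHSCT.** The study is descriptive, with no comparison planned (6.4, 8.9.1.4), and a proportion does answer an objective about the occurrence of transplant. The 6-to-30-month spread is what the rules permit, not what is known to have happened. The percentages illustrating its effect rest on assumed inputs. Horizons and competing-risk methods are often left to a statistical analysis plan, and none is shown. All of that is fair, and it limits how large the problem can be said to be. It does not remove it, because the protocol itself fixes an open-ended crude proportion, and it did fix a 6-month window for events of interest. It is also true that a crude proportion already counts patients who die untransplanted as not transplanted, so the main defects are the missing horizon and the treatment of incompletely observed patients.

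**On RFS.** A reader might infer that no responder can reach 6 months of RFS, or that the estimate is biased. The protocol supports neither. Six months is only a minimum and earlier starters can have far more. Kaplan-Meier censoring handles unequal follow-up at a cost in precision, not through bias by itself. Section 8.7.1.1 does speak loosely of RFS as a proportion, but 8.7.2.4 is specific about Kaplan-Meier. Section 8.9.3 already admits that small numbers limit that method.

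A reader might also want the minimum raised to about 8 months (6 months plus two 28-day cycles). That could exclude patients who fully inform both primary endpoints in a study of 15 to 30. It would still guarantee nothing, given gaps between cycles, censoring at the last remission date and truncation at trial entry.

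**Conclusion.** The alloHSCT point holds. The planned estimate has no horizon, while permitted opportunity runs from 6 to at least 30.6 months, so its value depends on start dates and reading dates. How far it moves cannot be determined from the protocol, because the start dates are not given. Under the assumed inputs the two extremes differ by 10 to 21 points (40 − 30 and 36 − 15). It should not be read as a finding that the cohort actually has that spread.

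The RFS point is arithmetically right but minor. The floor does not guarantee 6 months of RFS follow-up, yet under evenly spread starts it costs about one responder or fewer. Late-weighted starts would raise that number, but nothing in the protocol shows such a pattern.

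**What to change.** **In 8.7.2.4 (and the endpoint text in the Abstract and 8.3.2):**
- Make the main alloHSCT estimate the cumulative incidence at 6 months from first infusion, with death without transplant as a competing event and censoring at last contact or clinical-trial entry. If nobody is censored before 6 months, this reduces to the simple proportion transplanted by 6 months.
- Flag transplants preceded by other anti-leukaemic therapy given after BLINCYTO.
- Keep the proportion ever transplanted as a supplementary figure, reported with median follow-up.

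**For RFS:** leave the eligibility minimum as it is. Where possible, abstract the latest starters at the end of the enrolment window, which 8.2.1 already allows. Report the number at risk beside the 6-month RFS estimate.

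**Cost:** protocol wording, the order in which charts are read, and a check that the eCRF holds the transplant date and any therapy between BLINCYTO and transplant (8.3.3 lists only earlier treatment). Transplants after 6 months leave the main figure but remain in the supplementary one.

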8.2.2 Selection and Number of Sites

During feasibility assessment, 30 sites have been screened for inclusion in study.

Estimated that 7 sites will be enrolled in the study. These sites have confirmed that they can collect data on patients that are deceased.

8.2.3 Subject/Patient/Healthcare Professional Eligibility

8.2.3.1 Inclusion Criteria

- Adult patients (≥ 18 years at the initiation of BLINCYTO®) with Ph+ R/R B-Cell precursor ALL confirmed by either cytogenetics or molecular test
- Patients initiated BLINCYTO® at least 6 months prior to data abstraction
- Informed consent provided if required per local regulations

Note: Patients treated with TKIs in combination with BLINCYTO® are eligible.

Deceased patients at the time of data abstraction are eligible. An informed consent form (ICF), if required per local regulation needs to be signed on the day of enrollment and is required before chart abstractions can begin. Medical records of patients participating in clinical trials will be included up to the time the patient enrolls into a clinical trial, however patient data after enrollment in a clinical trial will not be collected.

8.2.3.2 Exclusion Criteria

- Medical records of patients with Ph- disease
- Medical records of patients who have received BLINCYTO® via an expanded access or compassionate use program

8.2.4 Matching

Not applicable.

8.2.5 Baseline Period

All baseline data to be abstracted will include a relevant medical history of covariates listed in Section 8.3.3 which predates BLINCYTO® initiation. If a covariate is not included in the pre-treatment time period, data may be collected for baseline data up to 3 days after initiation of BLINCYTO® treatment.

8.2.6 Study Follow-up

Follow up for objectives begins after the initiation of BLINCYTO® treatment. Eligible patients (including deceased) will include subjects who started BLINCYTO® treatment a minimum of 6 months prior to data abstraction. Treatment should have been initiated on or after approval of BLINCYTO® in China (December 2, 2020).

8.3 Variables

8.3.1 Exposure Assessment

Exposure in this study is the use of BLINCYTO® among patients with Ph+ R/R B-cell precursor ALL.

8.3.2 Outcome Assessment

Primary Outcomes

- CR/CRh rate within two cycles of BLINCYTO®. CR is defined as: < 5% bone marrow (BM) blasts, no evidence of extramedullary disease (EMD) and full recovery of peripheral blood counts defined as, platelets $\geq 100\,000/\mu\text{L}$, and absolute neutrophil count (ANC) $\geq 1000/\mu\text{L}$; CRh is defined as a CR with partial recovery of peripheral blood counts defined as platelets $> 50\,000/\mu\text{L}$ and $< 100\,000/\mu\text{L}$ and ANC $> 500/\mu\text{L}$ and $< 1000/\mu\text{L}$.
- Incidence of Adverse EOI. EOI are defined as: Cytokine release syndrome (CRS), BLINCYTO® associated neurological adverse event, and infection.

Secondary Outcomes

- BLINCYTO® use will be defined by BLINCYTO® treatment measured by number of cycles and duration of cycles. BLINCYTO® monotherapy and concomitant therapy with TKIs will be described.
- Occurrence of alloHSCT after BLINCYTO® treatment
- MRD status by flow cytometry or Polymerase Chain Reaction (PCR) within two cycles. MRD negativity is defined as: $<10^{-4}$ leukemic cells.
- OS is defined as the time from first infusion of BLINCYTO® until death due to any cause.
- RFS is defined for subjects who achieved CR/CRh within two cycles, as the time from first onset of CR/CRh until date of first documented relapse, or death due to any cause, whichever occurs first.

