6.2 Rationale

On 02 December 2020, the China National Medical Products Administration (NMPA) approved BLINCYTO® for the treatment of adult patients with R/R B-cell precursor ALL. The approval was based on the results from global studies that included Ph+ (Martinelli, 2017) and Ph- patients (Kantarjian, 2017), and the Phase 3 trial (NCT03476239) in China that demonstrated the efficacy and safety of BLINCYTO® in adult patients with Ph- R/R B-cell precursor ALL.

The Philadelphia chromosome (Ph), t(9;22) or (BCR-ABL), is present in approximately 25% of adults diagnosed with B-cell precursor ALL (referred to as Ph+ patients) (Liu-Dumlao, 2012; Liu, 2016). Tyrosine kinase inhibitors targeting the BCR-ABL oncogenic protein have been incorporated recently into most treatment regimens. Allogeneic hematopoietic stem cell transplantation (alloHSCT) remains the only curative option for patients with R/R disease. However, alloHSCT is only available to a subgroup of patients due to significant treatment-related morbidity and mortality. Therapies that enable adults with Ph+ R/R B-cell precursor ALL to achieve complete remission without complications from toxicities will allow patients to proceed to alloHSCT and improve survival (Saadeh, 2018).

The results from a phase 2 study for the treatment of 45 patients with Ph+ R/R B-cell precursor ALL (Study 20120216) provided evidence of the benefit of BLINCYTO® immunotherapy for a population of patients with an extremely poor prognosis (Martinelli, 2017). In Study 20120216, the primary efficacy endpoint was met as 35.6% of patients achieved complete remission/complete remission with partial hematological recovery (CR/CRh) in the first 2 treatment cycles, and the lower boundary of the 95% CI of 21.9% was > 10%. Overall survival of patients with Ph+ R/R B-cell precursor ALL in Study 20120216 was comparable with that observed for patients with Ph- R/R B-cell precursor ALL who received BLINCYTO® in global clinical trials. The safety results for patients with Ph+ R/R B-cell precursor ALL who received BLINCYTO® were consistent with those observed for patients with Ph- R/R B-cell precursor ALL.

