8.5 Study Size

The actual number of patients that will be included in the study will be dependent on the clinical use of BLINCYTO® at participating sites. We aim to collect data on approximately 15 to 30 patients initiating BLINCYTO® treatment for Ph+ R/R B-cell precursor ALL after commercial availability of BLINCYTO® in China, see Study Design Schema. The rationale for this sample size is based on the incidence of Ph+ status, constituting only about a quarter of B-cell precursor ALL patients, hence a relatively small number of cases can be recruited given that B-cell precursor ALL is a relatively rare disease. Additionally, the prior global clinical trial (Study 20120216; [Martinelli, 2017]) for the treatment of Ph+ R/R B-cell precursor ALL with BLINCYTO® studied 45 patients across sites in Europe and the US and we would expect smaller numbers over the planned study period in China. Further, 15 to 30 patients is a plausible estimate for an initial experience based on the expected clinical use of BLINCYTO® in China since being available in the country.

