8.7.2.4 Analysis of the Primary, Secondary, and Exploratory Endpoint(s) Analysis Set

Unless otherwise specified, all efficacy and safety analyses will be performed on the full analysis set (FAS), which will include all patients who received any infusion of BLINCYTO® in the study and met the inclusion/exclusion criteria.

General Principles

Analyses will be descriptive in nature. Demographic and patient characteristics will be summarized by descriptive statistics. Continuous variables will be summarized by n, mean, standard deviation, median, Q1 (25th percentile), Q3 (75th percentile), and ranges. Categorical variables will be summarized by counts and percentages for each category. Proportion and 95% CIs will be reported for patients with CR/CRh, MRD negative status, and alloHSCT.

For time-to-event outcomes, the Kaplan-Meier (K-M) method will be used to estimate the 6-month OS probability, including survival rates at selected timepoints (eg, 3- or 6-month, 12-month). The two-sided 95% CIs for proportion, median (if reached) and other quantiles of survival estimates will be constructed with using Brookmeyer method (Brookmeyer and Crowley, 1982), whereas the 95% CIs for survival rates at landmark timepoints will be calculated based on Greenwood's formula (Greenwood, 1926). The median of follow up time will be provided in addition and estimated by reverse K-M method (Schemper and Smith, 1996). K-M curves will also be presented.

Primary Analyses

- CR/CRh rate:

The best response within the first two cycles of BLINCYTO® treatment will be used to estimate the percentages of patients with CR/CRh. Patients without response assessment within two cycles of treatment will be considered as non-responders. The proportion of CR/CRh and its corresponding Clopper-Pearson 95% confidence intervals (CI) will be estimated.

- Incidence of adverse EOI

The patient incidence of adverse EOI (recorded within 6 months of first infusion of BLINCYTO®) will be summarized by categories (ie, cytokine release syndrome, BLINCYTO® associated neurological adverse event, or infection) and preferred term in descending order of frequency.

Secondary Analyses

- The duration of infusion (in days) and cumulative dose (in µg) of BLINCYTO® will be tabulated as continuous variable for each cycle and the whole infusion period. The number of cycles started and completed will be summarized descriptively. Reasons for treatment interruptions may also be provided per each reason when

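### The CRh definition caps both blood counts, so a marrow remission with one lineage fully and one partially recovered is neither CR nor CRh, and the primary response rate can be understated

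*Protocol*

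**What the plan says.** Section 8.3.2 defines CR by three elements: under 5% marrow blasts, no extramedullary disease, and "full recovery of peripheral blood counts defined as, platelets" of at least 100,000/µL with ANC of at least 1000/µL. It continues: "CRh is defined as a CR with partial recovery of peripheral blood counts defined as platelets" between 50,000 and 100,000/µL (both limits excluded) and ANC between 500 and 1000/µL (both limits excluded). The two bands are joined by a plain conjunction, so both must hold. The Abstract gives the same definition twice, in the objectives and endpoints table and in the list of outcome variables.

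Section 8.7.2.4 then fixes the analysis: "The best response within the first two cycles of BLINCYTO® treatment will be used to estimate the percentages of patients with CR/CRh". The only rule there for unclassified patients is "Patients without response assessment within two cycles of treatment will be considered as non-responders". On the interval it says "The proportion of CR/CRh and its corresponding Clopper-Pearson 95% confidence intervals (CI) will be estimated".

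RFS, in Sections 8.3.2 and 8.7.2.4, is confined to patients with CR/CRh within two cycles. It starts at onset of CR/CRh, and patients without relapse or death are censored at the latest date on which they are shown to remain in CR/CRh.

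**The concern.** CR and CRh together should cover every marrow remission whose counts exceed the lower CRh limits. As written they do not, because the upper limits in CRh apply to each lineage separately. A patient who improves in one lineage can lose responder status without gaining CR. The definition also contradicts itself: it makes CRh a kind of CR, while CR requires the full count recovery that CRh by definition lacks.

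This is the primary effectiveness endpoint, and the same classification selects the RFS population. The study is small: "We aim to collect data on approximately 15 to 30 patients initiating BLINCYTO® treatment". A single reclassified patient visibly moves the estimate. About seven sites are expected (Section 8.2.2), working from eCRF instructions (Section 8.3.4). If some apply the limits literally and others follow their own reading of CRh, the endpoint will mean different things at different sites.

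**Working it through.** **1. The Protocol's own response figure.** Section 6.2 reports for the prior phase 2 study of 45 patients that "the primary efficacy endpoint was met as 35.6% of patients achieved complete remission/complete remission with partial hematological recovery", with a lower 95% limit of 21.9%. Since 0.356 × 45 = 16.02, I take 16 responders. 16/45 = 35.56%, and the exact Clopper-Pearson interval is 21.87% to 51.22%. The stated rate and lower limit are reproduced. The figure serves below only as a plausible starting rate; no sample-size or power calculation depends on it.

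**2. The definitions applied literally**, taking under 5% blasts and no extramedullary disease as met:

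| Platelets (/µL) | ANC (/µL) | CR? | CRh? | Result |
|---|---|---|---|---|
| 120,000 | 1500 | yes | no | CR |
| 80,000 | 800 | no | yes | CRh |
| 80,000 | 1500 | no, platelets too low | no, ANC above its cap | neither |
| 120,000 | 800 | no, ANC too low | no, platelets above their cap | neither |

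The uncovered regions are (a) platelets above 50,000 and below 100,000 with ANC of 1000 or more, and (b) platelets of 100,000 or more with ANC above 500 and below 1000. If CRh instead meant both counts above their lower limits and CR counts not met, both regions would become CRh and no gap would remain above those limits.

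**3. Effect on the primary rate.** Moving one patient out of the numerator changes the rate by 1/n: 1/30 = 3.3 points and 1/15 = 6.7 points. As an illustration, assume that the rate with the gap closed is near 35.6%. Then 0.356 × 30 = 10.7, rounded to 11, and 0.356 × 15 = 5.3, rounded to 5. The number of patients still mixed at best response is an assumption; the Protocol gives none.

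| n | Mixed at best response | Responders counted | Rate | Clopper-Pearson 95% CI |
|---|---|---|---|---|
| 30 | 0 | 11 | 36.7% | 19.9 to 56.1 |
| 30 | 1 | 10 | 33.3% | 17.3 to 52.8 |
| 30 | 2 | 9 | 30.0% | 14.7 to 49.4 |
| 30 | 3 | 8 | 26.7% | 12.3 to 45.9 |
| 15 | 0 | 5 | 33.3% | 11.8 to 61.6 |
| 15 | 1 | 4 | 26.7% | 7.8 to 55.1 |
| 15 | 2 | 3 | 20.0% | 4.3 to 48.1 |

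**4. Effect on RFS.** A patient mixed throughout both cycles is left out of RFS. A patient who is mixed first and CR later enters RFS with a later onset date. A CRh patient with platelets steady at 80,000 whose ANC rises from 800 to 1500 has, read literally, left CRh without reaching CR, so the last date in CR/CRh used for censoring could be set too early.

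**5. Effect on MRD.** The objective in Section 7.2 speaks of MRD negativity after CR/CRh. The outcome in Section 8.3.2 refers to MRD status within two cycles with no response restriction. Section 8.7.2.4 adds none, and its default population is the full analysis set. The gap reaches MRD only if the denominator is limited to CR/CRh.

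**The case against.** The strongest reply is that the loss may be nil. Response is the best over two cycles, so a patient with mixed counts at one assessment may qualify as CR or CRh at another. This stands: only patients who are still mixed at best response are lost.

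Second, the Protocol does not say whether response is abstracted as the physician recorded it or worked out from counts. If physicians used a wider notion of CRh, the literal gap might never operate. That also stands as a limit on the size. It does not rescue the definition, because the recorded endpoint would then differ from the one the Protocol states.

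Third, the study is descriptive, with no hypothesis, threshold or powered sample size, and the intervals for 11 and 8 responders out of 30 overlap widely. No decision rule turns on the shift. However, the estimate is itself the primary result, and this error runs in one direction only.

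It cannot be left to a later analysis plan. The numerical limits are set in the Protocol, so a plan that follows them inherits the gap and one that departs from them contradicts the Protocol.

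A reader might go further and scale 35.6% down by some assumed share of mixed-recovery patients. The documents do not support that. They give no such share, and they do not give the CRh definition used in the prior study, so 35.6% may or may not already exclude these patients. A reader might also conclude that response must be derived centrally from laboratory values. The Protocol does not say that counts dated close to each marrow assessment are collected, and Sections 8.9.1.1 and 8.9.1.2 warn of incomplete recording and imprecise dates. Closing the gap does not require it.

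**Conclusion.** The definition is wrong as written in all three places, and no other passage repairs it. Marrow remissions with one lineage fully and the other partially recovered fall outside both CR and CRh, although they rank above CRh in recovery. Applied literally, the rule can lower the primary CR/CRh rate and cannot raise it. It can also remove patients from RFS and move RFS onset and censoring dates.

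The certain part is the direction and the cost per affected patient: 3.3 points at n = 30 and 6.7 points at n = 15. The number affected is unknown and may be zero. The tabulated rates rest on an assumed rate near 35.6% with the gap closed and on assumed counts of mixed patients. It would be too strong to say that the rate is understated by any particular amount, or that MRD is necessarily affected.

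**What to change.** In Section 8.3.2 and in both places in the Abstract, define CRh as under 5% marrow blasts, no extramedullary disease, platelets above 50,000/µL and ANC above 500/µL, with the CR count criteria not met. Remove the two upper limits and the words that make CRh a form of CR. Bring the eCRF completion instructions into line, so that all sites classify mixed recovery in the same way.

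The change keeps the Protocol's own lower limits and asks for no information beyond what the present definition already needs. The cost is one sentence in three places, the matching eCRF text, and the ethics approval that Section 11.1 requires for an amendment. It is best made before abstraction starts, since each chart is abstracted only once.
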